12.3 EFFICACY ANALYSIS

Objective tumor response will be tabulated overall. All participants who will be randomized to the PDT treatment or surgery will be evaluable for response. Tumor response will be evaluated according to RECIST v1.1. The treating physician will examine the clinical response and a photograph of the treatment site/s will be taken with paper ruler, to determine the reduction in the lesion size. Tumor response will be determined according to the guidelines in sections 9.2 and 9.3.

If clinically indicated, the clinical evaluation will be confirmed with pathological examination of tissue 3-mm punch biopsy that will be taken from the treated region.

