1.6 RISKS AND/OR BENEFITS

For participants that will have partial or complete response to PDT, the potential benefits include complete clinical regression of the tumor. Participants that do not respond to PDT may not benefit from this treatment. There is no guarantee of the outcome nor is it possible to predict whether or not the participant will respond to HPPH mediated PDT.

This is a Greater Than Minimal Risk study according to IRB criteria. The most likely potential risks associated with the PDT are short term edema and pain.

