4.3 MANAGEMENT OF THE NECK AND SALVAGE SURGERY

The management of the neck will be according to standard of care, at the discretion of the treating surgeon. If the participant, based on the pathology of the neck dissection or primary oral cancer resection, has perineural invasion, extracapsular spread, or requires additional therapies including radiation or chemotherapy, they will be dropped from the study and replaced with another participant.

Participants will receive standard curative therapy 6 weeks after failing to respond to PDT with HPPH. All the participants who will have disease progression, local recurrence, or partial or no response (PR, NR) following the PDT with HPPH will be considered treatment failures. The determination will be performed during the study visits, and based on clinical exam and pathology, if clinical exam is unclear.

The surgeon will provide a surgical plan for every patient, including those randomized to PDT. If the patient requires salvage surgery post-PDT, the surgeon will compare the salvage surgery specimen diameter to the diameter of the spot size used for PDT. This data will be used to demonstrate whether PDT affects the surgical plan.

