9.2 TARGET LESIONS

All identifiable lesions will be recorded with digital photography and clinical examination. The objective tumor response will be determined according to the following criteria per Recist v1.1:

- **Complete Response (CR):** Disappearance of all target lesions. Any lymph nodes must have a reduction in short axis to < 10 mm.

- **Partial Response (PR):** At least a 30% decrease in the sum of diameters of target lesions, taking as reference the baseline sum diameters. A biopsy will be taken from the suspected lesions for histological confirmation of squamous cell carcinoma.
- **Progressive Disease (PD):** At least a 20% increase in the sum of diameters of target lesions, taking as references the smallest sum on study (this includes the baseline sum if that is the smallest on study). In addition to the relative increase of 20%, the sum must also demonstrate an absolute increase of at least 5 mm. The appearance of one or more new lesions is also considered progression.
- **Stable Disease (SD):** Neither sufficient shrinkage to qualify for PR nor sufficient increase to qualify for PD, taking as reference the smallest sum diameters while on study, the response will be listed with stable disease. In this case, a biopsy will be taken from the suspected lesion for histological confirmation.

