12.1 JUSTIFICATION FOR THE STATISTICAL DESIGN AND THE NON-INFERIORITY MARGIN

In our previously published study we observed an 82% CR in patients with T1/T2 N0 SCC of the oral cavity treated with PDT and HPPH.¹⁸ We also reported a similar response rate when we used HPP-PDT to treat early stage laryngeal cancer.⁵² These response rates are in agreement with other studies using PDT in this indication (see **Table 1** in section **1.3**). All patients that failed to respond were successfully salvaged by surgery. Since the local recurrence rate after initial surgery is as high as 20%,⁷⁻⁹ we believe that it is reasonable to assume that 85% CR will be observed in both arms. We also wish to provide a bit of a cushion in case the surgical response rate is much higher than 85% given we are in an experimental setting.

In addition, we propose using the logic and rationale the FDA guidance documents propose for traditional phase III bioequivalence trials in terms of our trial design. The FDA refers to various rules such as the 80/20 rule, 75/75 rule, where the generic drug needs to be within 20% of the brand product relative to specified pharmaceutical measures. For a phase III trial the standard 80/20 rule translates to approximately a 17 percentage point difference. The 75/75 rule yields roughly a 21 percentage point difference. Hence, in the phase II setting we believe a 20-point difference is reasonable in terms of determining whether or not a confirmatory large-scale phase III trial with a tighter equivalence window should be put forward as a next step. The information gained from this study will be used for a larger scale phase III equivalence trial in terms of planning and sample size calculations with a tighter equivalence threshold. In terms of safety, it should be noted that patients that fail PDT can be effectively salvaged with surgery, in a timely manner.

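### The primary responder is never defined: 12.3 points to RECIST categories that include partial response, while 12.1 plans on complete response and 4.3 treats partial response as failure, for PDT only

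*Combined protocol and SAP*

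**What the plan says.** - **Objective and hypotheses (3.1, 12.2).** The primary comparison is the rate of tumor response at 24 months. Neither section defines a responder.
- **Analysis (12.3).** "Objective tumor response will be tabulated overall", and "Tumor response will be determined according to the guidelines in sections 9.2 and 9.3". Section 4.3 is not cited.
- **Classification (9.2, 9.3).** "The objective tumor response will be determined according to the following criteria per Recist v1.1"; the list is CR, PR, PD and SD. PR is "At least a 30% decrease in the sum of diameters of target lesions, taking as reference the baseline sum diameters", so residual tumour is compatible with it. For PD, "In addition to the relative increase of 20%, the sum must also demonstrate an absolute increase of at least 5 mm"; a new lesion is also PD. Section 9.3 adds best overall response over the whole study and does not relate it to the 24-month endpoint.
- **Planning (12.1, 12.2).** "we believe that it is reasonable to assume that 85% CR will be observed in both arms". Section 12.2 carries the same 85% into the power statement as a tumor response probability.
- **Failure rule (4.3).** Disease progression, local recurrence, or "partial or no response (PR, NR) following the PDT with HPPH will be considered treatment failures". There is no matching rule for surgery.
- **Risk/benefit text (1.6).** "For participants that will have partial or complete response to PDT" groups the two categories, although this sentence does not define an endpoint.

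**The concern.** Two competent analysts could follow these sections and report different primary results. One would count CR only, relying on 12.1 and 4.3. The other would count CR plus PR, because 12.3 sends the reader to a RECIST list in which PR is a grade of response.

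The choice does not affect the arms equally. After excision no target lesion remains to shrink, so PR is in practice available only to PDT. Counting it would move the comparison toward non-inferiority and detach the test from the CR rate on which it was planned. The trial is open-label and the treating physician assesses response, so the definition should not be left open until data are in hand.

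**Working it through.** **Inputs.** 57 per arm, margin 20 points, 85% in both arms, Farrington-Manning score test, nominal 0.05 (12.2). The only statement that tests are two-sided stands in the quality-of-life paragraph of 12.2, so both one-sided 0.025 and 0.05 are shown.

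**1. The plan's own power figure.** Power = Φ{[(pT − pC + Δ) − z·s0] / s1}. Here s0 is the standard error at the restricted estimates under the null, and s1 the standard error at the true rates.
- Restricted estimates: 0.708 (PDT) and 0.908 (surgery).
- s0 = √[(0.7077×0.2923 + 0.9077×0.0923)/57] = 0.0714.
- s1 = √[2×0.85×0.15/57] = 0.0669.
- One-sided 0.025: (0.20 − 1.96×0.0714)/0.0669 = 0.898, power 81.5% (exact enumeration 83.2%).
- One-sided 0.05: 89.1% (exact 89.8%).

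The stated 80% or so is reproduced at one-sided 0.025, with the 85% that 12.1 calls CR.

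**2. What the 85% stands for.** The summary row of the literature table in 1.3 gives CR 619/729 = 84.9% and CR+PR (619 + 97)/729 = 98.2%. The planning rate matches CR, not CR+PR.

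**3. Error if PR counts in the PDT arm only.** Set true CR at the margin: 65% PDT, 85% surgery. Add the PR share to the PDT rate and enumerate the score test exactly over both binomials with 57 per arm.

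| PR share counted in PDT | Source | PDT rate analysed | False non-inferiority, one-sided 0.025 | One-sided 0.05 |
|---|---|---|---|---|
| 0 | CR only | 65.0% | 2.6% | 5.2% |
| 5 points | assumed | 70.0% | 9.5% | 16.4% |
| 1/17 = 5.9% | HPPH at 140 J/cm², 1.5.3 | 70.9% | 11.7% | 19.4% |
| 10 points | assumed | 75.0% | 26.6% | 38.3% |
| 97/729 = 13.3% | literature table, 1.3 | 78.3% | 44.4% | 57.1% |

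**4. How far to trust the PR shares.**
- The 18 non-HPPH rows of the literature table add to n = 729 and PR = 97, exactly the printed totals. With the HPPH row they would be 746 and 100. So 97/729 contains no HPPH patient.
- For the HPPH study that table shows 14 CR and 3 PR, while 1.5.3 shows 14 CR, 1 PR and 2 SD at 140 J/cm². In the one study that can be checked, the PR column seems to include stable disease.
- The HPPH share is the relevant one, but it is a single lesion among 17.
- All the sourced shares are used as proxies for PR at month 24. The HPPH and literature figures describe early response, and 4.1.2 and 4.3 provide for standard therapy after PR, so persistent PR at 24 months should be less common.

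**The case against.** The strongest reply is that CR is plainly meant. Section 12.3 never says that PR counts, and 9.2 uses objective tumor response as the name of a classification that also holds SD and PD. Where the protocol attaches a number, response means CR: the literature rate of 0.85 in 1.3 is a CR ratio, section 2 sets 85% CR beside surgical cure rates, and 4.3 calls PR a failure. This stands as evidence of intent. A reader might infer that 12.3 adopts CR+PR as the endpoint, and the documents do not support that. But 12.1 is a planning assumption, 4.3 covers salvage in one arm, and the section that governs the analysis cites neither. The responder remains undefined.

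A reader might also infer that a small recurrence after PDT would be scored as a response. For example, a 20 mm tumour clears and regrows to 4 mm: it is 80% below baseline and under the 5 mm PD threshold. The text does not establish this. A new lesion is PD in both arms under 9.2 and Table 4, and 4.3 makes local recurrence after PDT a failure. What remains is a secondary ambiguity, because 9.2 does not say whether regrowth at the treated site is a new lesion or the target lesion.

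Finally, it can be said that few PRs will persist to month 24. That is fair, and it limits the size. It also exposes a second gap: the plan does not say how to score a PDT failure who is clear at 24 months after salvage surgery. Section 2 reports that all earlier T1/T2 patients without CR were salvaged, so this route may matter more than persistent PR.

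**Conclusion.** The point holds as an undefined primary responder with conflicting passages, not as a decision to count PR. Read as written, 12.3 could credit PDT with residual tumour as response, in a category with little meaning after surgery.

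With true CR at the margin and PR counted in PDT only, the HPPH share of 1/17 takes false non-inferiority from 2.6% to about 12% at one-sided 0.025. The 27 to 44% at PR shares of 10 to 13% are upper bounds and not a forecast, since those shares are assumed or come from early, non-HPPH data before salvage. All of these figures assume no PR in the surgery arm and that early PR shares carry to month 24. The existence of the gap does not depend on them.

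**What to change.** - In 3.1, 9.1, 12.2 and 12.3, define the primary responder in both arms as a participant in complete response at 24 months with no earlier treatment failure.
- Count as non-response: PR, SD or no response, PD, local recurrence in the treated or resected field, and salvage therapy given for failure, even if the participant is clear at 24 months after salvage.
- For the analysis, apply the failure definition in 4.3 to both arms, and reconcile 4.3, 9.2, 9.3 and 12.3. Local recurrence then counts as non-response whether or not 9.2 would call it a new lesion. This concerns how outcomes are counted, not how patients are managed.
- Keep CR+PR and best overall response as descriptive tables only.

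**Cost.** Wording in the protocol and analysis sections, settled before outcome data are seen. There are no added patients, visits or procedures. The 57 per arm and the stated power are unchanged because they were planned on CR. The downside is that the PDT response rate may look less favourable than it would with PR or salvaged patients included.

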12.4 ADVERSE EVENT

The frequency of toxicities will be tabulated by grade. All participants who receive any study treatment will be considered evaluable for toxicity.

RPCI may terminate the study at any time upon immediate notice if it believes termination is necessary for the safety of participants enrolled in the study.

12.5 INTERIM ANALYSIS AND CRITERIA FOR EARLY TERMINATION OF THE STUDY

No interim analysis is planned for this study.

13 ETHICAL AND REGULATORY STANDARDS

13.1 ETHICAL PRINCIPLES

This study will not be initiated until the protocol and informed consent document(s) have been reviewed and approved by a properly constituted Institutional Review Board (IRB) or Independent Ethics Committee (IEC). Each participant (or legal guardian) shall read, understand, and sign an instrument of informed consent prior to performance of any study-specific procedure. It is the responsibility of the investigator to ensure that the participant is made aware of the investigational nature of the treatment and that informed consent is given.

The Investigator is responsible for the retention of the participant log and participant records; although personal information may be reviewed by authorized persons, that information will be treated as strictly confidential and will not be made publicly available. The investigator is also responsible for obtaining participant authorization to access medical records and other applicable study specific information according to Health Insurance Portability and Accountability Act regulations (where applicable).

This study will be conducted in compliance with all applicable laws and regulations of the state and/or country and institution where the participant is treated. The clinical trial should be conducted in accordance with the ethical principles embodied in the Belmont Report: Ethical Principles and Guidelines for the Protection of Human Subjects of Research, consistent with good clinical practice and the applicable regulatory requirements and according to the guidelines in this protocol, including attached appendices.

13.2 INFORMED CONSENT

The Investigator (or IRB specified designee) is responsible for obtaining written consent from each participant or the participant's legally authorized representative in accordance with applicable GCP guidelines using the approved informed consent form, before any study specific procedures (including screening procedures) are performed. The informed consent form acknowledges all information that must be given to the participant according to GCP guidelines, including the purpose and nature of the study, the expected efficacy and possible side effects of the treatment(s), and specifying that refusal to participate will not influence further options for therapy. Any additional information that is applicable to the study must also be included. Additional national or institutionally mandated requirements for informed consent must also be adhered to. The participant should also be made aware that by signing the consent form, processing of sensitive clinical trial data and transfer to other countries for further processing is allowed.

The Investigator shall provide a copy of the signed consent form to the participant and the signed original shall be maintained in the Investigator File. A copy of the signed consent form must be filed in the participant file. At any stage, the participant may withdraw from the study and such a decision will not affect any further treatment options.

14 STUDY RESPONSIBILITIES

14.1 DATA COLLECTION

Data entry into the database is to be completed in a timely fashion (within 30 days) after the participant's clinic visit. If an AE is considered serious it is captured on both the Adverse Event page and the Serious Adverse Event Form, which is handled in an expedited fashion).

Data management activities will be performed using EXPeRT. EXPeRT is a suite of software tools that enables the collection, cleaning and viewing of clinical trial data. CRS data management will design the study-specific database and facilitate its development by the eClinical Information Technology team. Once the database design is approved by the Investigator, Statistician, and Clinical Research Coordinator, the database will be put into production and data entry can begin. Data can be entered and changed only by those with the rights to do so into the eCRFs (via EXPeRT Module). eClinical is compliant with all relevant technical aspects of relevant GCP guidelines.

- The system can generate accurate copies of stored data and audit trail information in human readable form.
- System access is limited to authorized individuals through the controlled assignment of unique ID and password combinations.
- The system is designed to periodically force users to change their passwords and verifies that user ID and password combinations remain unique.
- The system automatically generates a permanent time-stamped audit trail of all user interactions.

When data entry is complete, data management will review the data and will query any missing, incomplete, or invalid data points for resolution by the Clinical Research Coordinator and Investigator. Once all queries have been resolved, the data can be released to the statistician for analysis.

14.2 MAINTENANCE OF STUDY DOCUMENTS

Essential documents should be retained per RPCI's policy for 6 years from the study termination date. These documents could be retained for a longer period, however, if required by the applicable local regulatory requirements or by an agreement with RPCI.

15 ADMINISTRATIVE RULES

15.1 REVISIONS TO THE PROTOCOL

RPCI may make such changes to the protocol as it deems necessary for safety reasons or as may be required by the U.S. FDA or other regulatory agencies. Revisions will be submitted to the IRB/ERC for written approval before implementation.

15.2 TERMINATION OF THE STUDY

It is agreed that, for reasonable cause, either the Investigators or the Sponsor, RPCI may terminate this study, provided a written notice is submitted within the time period provided for in the Clinical Trial Agreement. In addition, RPCI may terminate the study at any time upon immediate notice if it believes termination is necessary for the safety of patients enrolled in the study.

15.3 CONFIDENTIALITY

Any data, specimens, forms, reports, photos, and other records that leave the site will be identified only by a participant identification number (Participant ID, PID) to maintain confidentiality. All records will be kept in a limited access environment. All computer entry and networking programs will be done using PIDs only. Information will not be released without written authorization of the participant.

2. INFORMED CONSENT

- Informed consent must be obtained by the site Investigator/designee from any participant, or their legally authorized representative, wishing to participate, prior to any procedures or treatment.
- An informed consent template is provided by RPCI and can be amended to reflect institutional requirements.
- All consent changes must be reviewed by RPCI Network Office prior to submission to the site IRB.
- The informed consent must be IRB approved.
- Always check that the most up to date version of the IRB approved consent is being used.
- Within 5 business days, notify the RPCI Network Office of all participant withdrawals or consent to limited study participation and appropriately document the discontinuation and the reason(s) why.

3. PARTICIPANT REGISTRATION

The participant, or their legally authorized representative, completes the **Gender, Race, and Ethnicity Form** and this is placed in the study binder.

RPCI does not grant exceptions to eligibility criteria.

Phase 2 Protocol Registration Instructions

The Screening and Enrollment Log must be faxed to the RPCI Network Office within 1 business day of the date the participant is consented. Once the Investigator has determined that eligibility has been met, complete the Subject Registration Form and fax it to the RPCI Network Monitor at [contact].

Protocol Randomization Instructions

4. Patients at Roswell Park Cancer Institute will be registered directly by Roswell staff using the web-based registration system. For patients at institutions outside Roswell Park Cancer Institute, the local site staff will contact the appropriate coordinator to register the patient using the web-based registration application as developed by the GOG Foundation Statistical & Data Management Center in conjunction with the study biostatistician. Within 24 hours the Network Monitor will email the randomization arm assignment and network participant ID # back to the site PI. The site PI will send a confirmation email back to the Network Monitor verifying the randomization arm for the specified network participant. Questions regarding randomization issues can be emailed to [contact] or [contact].

5. STUDY DEVIATIONS

- If a deviation has occurred to eliminate hazard, this must be reported to the RPCI Network, site IRB and any other regulatory authority involved in the study.
- ALL study deviations will be recorded on the **Study Deviation Log**.

6. STUDY DOCUMENTATION

- Study documents must be filled out completely and correctly. Ditto marks are not allowed.
- If an entry has been documented in error put a single line through the entry and initial and date the change. The RPCI Network Monitor must be able to read what has been deleted.
 - Do **NOT** use white-out, magic marker, scratch-outs.
 - Do **NOT** erase entries.
- Use only black ink for documentation on the accountability form and any other study forms.
- It is the responsibility of RPCI to inform the Investigator/institution as to when these documents no longer need to be retained. If, for any reason, the Investigator desires to no longer maintain the study records, they may be transferred to another institution, another investigator, or to RPCI upon written agreement between the Investigator and RPCI.

